- **H2:** A higher proportion of the new NF swabs with 5 cm insertion will be adequate for cytopathology interpretation compared to the NF swab for 3 cm insertion.
- **H3:** The new NF swab will have molecular adequacy that is commensurate with the original NF swab used in the PAC Self-Swab Study.
- **H4:** The new NF swab will have acceptability/pain performance commensurate with the originally proposed NF swab and the 5 cm insertion depth will have similar acceptability/pain performance as the 3 cm insertion depth.

Our expected outcomes are cytological and molecular preliminary performance characteristics of the new NF swab in addition to user acceptability. These outcomes will help ensure the use of a viable swab in SOLO that is relevant in future anal cancer screening programs.

B Pilot Study Objective and Endpoints

B.1 Pilot Study Objective

To ensure the use of a swab in SOLO that is comparable to the originally proposed swab for SOLO, determine the preliminary performance characteristics of the new NF swab.

B.2 Pilot Study Endpoints

1. A comparison of the proportions of individuals who collect squamocolumnar cells when using a NF swab with a 5 cm vs. a 3 cm insertion depth.
2. A comparison of the proportions of individuals who collect cytologically adequate specimens when using a NF swab with a 5 cm vs. a 3 cm insertion depth.
3. A comparison of the proportions of individuals who collect adequate specimens for molecular genotyping when using the new NF swab vs. the original swab used in the PAC Self-Swab Study.
4. A comparison of the acceptability and pain performance of the new NF swab vs. the original swab and the 5 cm and 3 cm insertion depth.

C Pilot Study Eligibility

The pilot study team will evaluate eligibility according to the following criteria. Individuals must meet all inclusion and none of the exclusion criteria to be registered on to the pilot study. Any questions or concerns regarding eligibility should be directed to the PI, [name] ([contact]).

C.1 Inclusion Criteria

A potential pilot study subject who meets all of the following inclusion criteria is eligible to participate in the pilot study. Note that these criteria apply regardless of HPV vaccination status or disability status.

1. Aged \geq 35 years.
2. Must be either:
 - a) A cisgender or transgender sexual minority man, or
 - b) A transgender woman who has sex with men.
3. Resides in the Milwaukee metropolitan area.
4. Speak and understand English.

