5. Ability to understand a written informed consent document, and the willingness to sign it.
NOTE: this inclusion criterion is mandatory unless a waiver of the informed consent process and document is being requested.

C.2 Exclusion Criteria

A potential pilot study subject who meets any of the following exclusion criteria is ineligible to participate in the pilot study.

1. Presence of any contraindicating severe anal disease or condition, e.g., anal stenosis.

D Pilot Study Accrual Goals and Study Duration

A total of 60 SGM will be recruited from the greater Milwaukee metropolitan area. Accrual will last for approximately 2 months.

The pilot study will reach pilot study completion within 4 months of the beginning of accrual.

E Subject Recruitment and Registration

E.1 Recruitment

Potential SGM participants will be recruited first from the group of individuals who consented into the PAC Self-Swab Study (PRO00032999) and then indicated an interest in a follow-up study (n=126). We will enroll those aged \geq 35 years. Persons reporting no sex with men during the last five years will be included if they identify as an SGM individual.

If the initial recruitment results in fewer than 60 people, we will recruit by other means:

1. Advertising on geo-located social/dating apps commonly used by older SGM, e.g., Scruff, Growlr, and Jack'd. We will run advertisements on the apps using a 25-mile radius from the city center in Milwaukee to reach people throughout the city's metro area.
2. The use of print materials in gay-friendly business and a website (mindyourbehind.org) used in the PAC Self-Swab Study. The material will mention the study is recruiting for an anal cancer screening study.

Recruitment material will be approved by an MCW Institutional Review Board (IRB). The SOLO Study Coordinator in Milwaukee will oversee recruitment activity. We will record recruitment activities.

E.2 Consenting

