Potential participants will be screened using an online computer-assisted self-interview (CASI). Those who are eligible will be asked to leave contact information. Study staff will contact eligible individuals, provide an overview of the pilot study, and invite the individual to a schedule a consenting session which will be followed by the cytology screening at the Curative Building on the MCW campus. Those who are not eligible will be thanked for their interest and provided links to vetted anal cancer education websites. Minimal Protected Health Information (PHI) will be collected in the eligibility survey.

At the consenting session staff will first ask the eligible individual to confirm their email address, name, and birthdate. The session will occur in a closed office and include information about 1) high rates of anal cancer in SGM, 2) anal cancer screening and the role of swabbing, 3) pilot study activities, and 4) the potential harms and benefits of participation. The staff member obtaining consent will emphasize that participation is voluntary and that participants can choose to join and,

if desired, leave the pilot study at any point without any repercussions. The ICF will also notify individuals that we will collect their street address to support payment using the MCW visa card.

Prior to obtaining their signature, the staff member will ask the individual if they have any questions and, if not, to briefly review their understanding of their participation by asking simple questions about the pilot study to be sure the information was clearly understood.

Individuals agreeing to provide consent will sign an ICF hard copy. It will be photocopied with the copy given to the participant.

F Pilot Study Design and Intervention

F.1 Study Design

This pilot feasibility study will use a randomized controlled trial design.

Figure 1 illustrates the pilot study design.

F.2 Randomization

Consented individuals will be randomized to either the intervention (5 cm insertion depth) or the control (3 cm insertion depth) arm using a number generator in REDCap. If the number is .0000 to .4999, the individual will be assigned to the intervention condition. If the number is .5000 to .9999, the individual will be assigned to the control condition.

The participant is considered enrolled in the pilot study when they sign a consent form and are randomized to either the intervention or control arm.

F.3 Cytology Sampling

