1. A comparison of the proportions of individuals who collect squamocolumnar cells when using a NF swab with a 5 cm vs. a 3 cm insertion depth.
2. A comparison of the proportions of individuals who collect cytologically adequate specimens when using a NF swab with a 5 cm vs. a 3 cm insertion depth.
3. A comparison of the proportions of individuals who collect adequate specimens for molecular genotyping when using the new NF swab vs. the original swab used in the PAC Self-Swab Study.
4. A comparison of the acceptability and pain performance of the new NF swab vs. the original swab.

H.2 Power for Endpoints

This pilot feasibility study does not have the power to make conclusive statements about the study endpoints.

H.3 Analysis Plan

H.3.1 Preliminary analyses

We will assess the success of randomization. For surveys, we will calculate item response rates for each arm of the study and for subgroups based on HIV status, race/ethnicity, and education.⁴³

After evaluating missing survey data, we will use multiple imputation⁴⁴ to maintain the maximum sample size if data are missing at random. Sensitivity analyses will compare results if data are not missing at random.⁴⁵

In each study arm, we will analyze frequencies of survey items, demographics, other domains, adverse events, and serious adverse events.

H.3.2 Primary Endpoint 1

The presence of cells from the squamocolumnar junction will be assessed in each specimen (Yes/No). Proportions of specimens with squamocolumnar cells will be compared for the 5 cm and 3 cm swabs.

H.3.3 Primary Endpoint 2

Cytologic adequacy is defined as the presence of ~2000-3000 nucleated squamous cells. Proportions of adequate specimens will be compared for the 5 cm and 3 cm swabs.

H.3.4 Primary Endpoint 3

The PAC Self-Swab Study molecular adequacy estimates, given study size, were quite precise with narrow confidence limits. The estimates derived from this pilot study will have wider confidence limits. The original and new swabs will be considered to have commensurate molecular adequacy if the exact confidence limits of the original PAC Self-Swab Study swab are covered by the exact confidence limits of the piloted swab.

H.3.5 Primary Endpoint 4

Each participant will receive a short cytology CASI immediately after the cytology screening to rate their acceptability of the cytology screening on a Likert scale and pain on a visual scale.³⁷ Proportions of individuals' ratings for adequacy and pain will be compared for

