- 1) the 5 cm and 3 cm swabs, and
- 2) the new NF swab vs the original swab.

The Exact 95% confidence limits surrounding proportions for acceptability and pain will be compared for overlap for 5 cm vs 3 cm insertion depths.

The comparison of acceptability/pain between the new NF swab and the original swab will be analyzed as in H.3.4.

I ADVERSE EVENTS AND OTHER REPORTABLE INCIDENTS

This study is low risk to participants due to its design and the nature of the intervention being tested (i.e., cancer screening and behavioral interventions). No investigational drugs or devices are involved.

Even though this study does not test a therapeutic intervention, this study will follow the Cancer Therapy Evaluation Program (CTEP) guidelines for reporting of adverse events. All expedited adverse event reports are required to be submitted to the MCW Institutional Review Board (IRB).

I.1 Definitions

I.1.1 Adverse Event (AE)

Any untoward medical occurrence in an individual or clinical investigation subject administered an interventional product and which does not necessarily have to have a causal relationship with this intervention.

This study will utilize the NCI Common Terminology Criteria for Adverse Events (CTCAE) version 5.0, located on the CTEP web site:

https://ctep.cancer.gov/protocolDevelopment/electronic_applications/ctc.htm

AEs may be spontaneously reported by the subject and/or in response to an open question from study personnel or revealed by observation, physical examination or other diagnostic procedures.

I.1.2 Serious Adverse Event (SAE)

Serious Adverse Event (SAE) means any untoward medical occurrence that results in any of the following outcomes:

- **Death.** Results in death.
- **Life-threatening.** Is life-threatening (refers to an AE in which the participant was at risk of death at the time of the event. It does not refer to an event which hypothetically might have caused death if it were more severe).
- **Hospitalization.** Requires inpatient hospitalization ≥ 24 hours or prolongation of an existing hospitalization.
- **Disability/incapacity.** Results in persistent or significant disability or incapacity. (Disability is defined as a substantial disruption of a person's ability to conduct normal life functions).
- **Pregnancy**

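### Graded acceptability and pain ratings are compared between 5 cm and 3 cm only as proportions, with the category or cut unstated, so their ordering is discarded

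*Combined protocol and SAP*

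**What the plan says.** H.3.5 (Primary Endpoint 4) has participants complete a short survey straight after self-sampling and "rate their acceptability of the cytology screening on a Likert scale and pain on a visual scale". The number of Likert levels and the range of the visual scale are not given.

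The analysis then works with proportions only. The individuals' "ratings for adequacy and pain will be compared for" two contrasts: 5 cm against 3 cm, and new swab against original. (Adequacy stands there where acceptability is evidently meant.) For the depths the rule is: "The Exact 95% confidence limits surrounding proportions for acceptability and pain will be compared for overlap for 5 cm vs 3 cm insertion depths". For the swabs: "The comparison of acceptability/pain between the new NF swab and the original swab will be analyzed as in H.3.4", which again calls for exact limits on a proportion.

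No section says which ratings count as acceptable or as painful, or gives a cut-point. No mean, rank-based or ordinal comparison is planned. H.3.1 plans item frequencies by arm, as description.

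The hypothesis served is H4 in Section A, which expects that "the 5 cm insertion depth will have similar acceptability/pain performance as the 3 cm insertion depth", with no margin. The depth contrast appears in endpoint 4 of B.2 and in H.3.5, although the restatement in H.1 names only the new and original swabs. H.2 adds: "This pilot feasibility study does not have the power to make conclusive statements about the study endpoints".

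**The concern.** Endpoints 1 to 3 each rest on a defined yes/no outcome: junction cells seen or not, a squamous cell count, and detection of human RNase P (F.4). Endpoint 4 starts from graded ratings and turns them into proportions without saying how. Two things follow.

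- The information in the ordering is lost. A shift from mild to moderate pain is invisible unless it crosses the chosen line.
- The line is not fixed, so both the answer and the amount of information lost depend on a choice that could be made after the data are seen.

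The direction matters. The Background names reduced acceptability as the possible drawback of deeper insertion, while H4 predicts no material difference. An analysis that makes a real difference in discomfort harder to see leans toward H4. K.5.2 says the pilot informs whether the 3 cm or 5 cm swab is useful for the parent study. The problem is separate from the overlap rule: it would remain if that rule were replaced by an interval for a difference in proportions.

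**Working it through.** **Figure to reproduce.** None. The documents give no power calculation, effect size, standard deviation or rating distribution.

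**Inputs from the documents.** Section D: "A total of 60 SGM will be recruited from the greater Milwaukee metropolitan area". F.2: "If the number is .0000 to .4999, the individual will be assigned to the intervention condition", otherwise control. This is simple 1:1 randomisation, so 30 per arm is expected (binomial 95% range 22 to 38).

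**Assumptions, not in the documents.** 30 per arm, two-sided 5%, and either a normal pain score with a 0.7 SD shift or proportional-odds ratings with the distributions shown.

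**Step 1: information kept by a binary split of a normal score.** With share p on one side, the fraction kept is φ(z_p)² / [p(1−p)].

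- 50/50: 0.3989² / 0.25 = 0.637. Loss 36%; 60 people act like 38.
- 80/20: 0.2800² / 0.16 = 0.490. Loss 51%; 60 act like 29.
- 90/10: 0.1755² / 0.09 = 0.342. Loss 66%; 60 act like 21.

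The median split is the best case, so 36% is the minimum loss under normality.

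**Step 2: what that does to power.** On the score, the noncentrality is 0.7 × √(30/2) = 2.71 and t-test power is 76%. For the splits, the pooled two-proportion z-test was enumerated exactly over all outcomes at 30 per arm. The plan specifies neither test; they only put the two analyses on one footing.

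| Split | Proportions above the cut | Power |
|---|---|---|
| Median, cut midway between the arms | 36.3% vs 63.7% | 58% |
| Median of the lower-scoring arm | 50.0% vs 75.8% | 54% |
| 80/20, cut 0.84 SD above the midpoint | 11.7% vs 31.1% | 46% |
| 80/20, set in the lower-scoring arm | 20.0% vs 44.4% | 53% |

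Other definitions of an 80/20 split go lower: 44% if 20% of both arms together lie above the cut (10.7% vs 29.3%), and 38% if the cut sits in the opposite tail (20% vs 6.2% below it).

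**Step 3: Likert ratings.** Under proportional odds, a cut with share p on one side keeps p(1−p) / [(1 − Σp_i³)/3] of the information in the ordered scale.

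- Five equal levels: the denominator is (1 − 0.040)/3 = 0.320. A 40/60 cut keeps 0.24/0.320 (loss 25%); a 20/80 cut keeps 0.16/0.320 (loss 50%).
- Levels 50/30/10/6/4%: the denominator is 0.282. A cut at 50% keeps 0.25/0.282 (loss 11%); at 96% it keeps 0.0384/0.282 (loss 86%).
- Levels 70/20/6/3/1%: the denominator is 0.216. A cut at 70% keeps 0.21/0.216 (loss 3%); at 99% it keeps 0.0099/0.216 (loss 95%).

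**Step 4: pain with a share s at zero, the rest continuous, split at any pain.** The denominator becomes (1 − s³)/3.

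- s = 0.4: 0.24/0.312 kept, loss 23%.
- s = 0.5: 0.25/0.292 kept, loss 14%.
- s = 0.7: 0.21/0.219 kept, loss 4%.

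**The case against.** Much of the case against the concern is fair.

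- **No single figure applies.** A reader might infer that a third or more of the information is lost on both scales. The documents do not support that: they give no distribution, number of levels or cut. A Likert item is not a normal score, and K.5.1 describes the swab as possibly uncomfortable with occasional minor bleeding, so pain scores crowded at zero are plausible. Steps 3 and 4 show losses well below a third, and others far above it. This stands, and the size must be stated conditionally.
- **Dichotomisation is never named.** The text could mean the proportion at each rating level. That also stands, but it does not rescue the plan. Comparing levels one at a time still ignores their order, and the levels are still unspecified.
- **H.2 disclaims conclusive power.** This lowers the stakes, because the pilot is not a confirmatory test. It does not define the outcome, and a small study has most reason to keep the information it collects. H.3.1's frequencies show the ratings by arm but give no between-arm estimate.
- **Proportions are needed for the comparison with the PAC swab.** True under the H.3.4 rule, and K.6.3 says the survey items come mainly from the PAC surveys. A PAC cut may exist, but it is not in these documents. In any case, that need does not bind the depth comparison, which is made within this trial.
- **The 0.7 SD shift is assumed.** It is, and the power figures are illustrative only.

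**Conclusion.** The concern holds in a conditional form. H.3.5 collects ordered ratings and compares the two depths only through proportions, discarding the ordering and leaving the category or cut unstated. If pain scores are roughly normal, any binary split loses at least about 36% of the information. At an assumed 0.7 SD shift and 30 per arm, power is 76% on the score, about 54-58% after a median split and about 46-53% after an 80/20 split under the two definitions tabulated. For Likert or zero-heavy ratings the loss depends on the cut, from a few percent to most of the information. The loss leans toward the similarity that H4 predicts.

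Two further inferences should be resisted. The documents do not show that anyone means to choose the cut after seeing results; they only leave room for it. And the weakness of judging by overlap of exact limits is a separate matter that should not be added to the loss described here. This is a change the plan should make, tempered by its pilot status.

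**What to change.** In H.3.5, for 5 cm versus 3 cm:

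- **Pain:** estimate the difference on the visual scale as a mean difference, or a Hodges-Lehmann shift if scores are skewed, with a 95% CI. State beforehand how skewness will decide between them.
- **Acceptability:** estimate an ordinal effect, either the Mann-Whitney probability or a proportional-odds ratio, with a 95% CI. Name one.
- Present both as preliminary, in line with H.2.

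Keep proportions as a descriptive summary and for the comparison with the PAC swab. For these, fix one cut per item before data review and apply it identically to both studies. State the range of the visual scale and the number of Likert levels, and replace adequacy with acceptability in the analysis sentence if that is what is meant.

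The cost is analysis wording and slightly more analysis work. The ratings are collected in any case, and neither the sample size nor any study procedure changes.

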An important component of SOLO is the testing of two different kinds of swabs, nylon-flocked and Dacron, for molecular and cytological adequacy and end user acceptability within a self-sampling and clinician-sampling context. We chose a nylon-flocked (NF) swab for use in SOLO given its high adequacy in our prior study: the Prevent Anal Cancer (PAC) Self-Swab Study (R01 CA215403, PI: [name]); however, this NF swab is unlikely to be available for clinical use in the future due to recent changes in the manufacturer's priorities. Since SOLO results need to be widely generalizable and relevant to anal cancer screening, we need to use a different NF swab model and assess its cytological and molecular performance characteristics in a pilot study before beginning SOLO. Given our prior success with a NF swab developed by Copan Italia s.p.a. (Brescia, Italy) we will test the feasibility of a new Copan swab developed for anal cancer screening.

We will test the cytological performance of the swab at two insertion depths, 3 cm and 5 cm, to determine which insertion depth is better at collecting cells from the squamocolumnar junction (SCJ), an anatomic site that is particularly vulnerable to carcinogenic transformation. We hypothesize that the 5 cm insertion will result in a higher quality specimen with cells from the SCJ. However, the deeper swab insertion may affect end user acceptability without increasing adequacy or quality.

We will test the new swab with 60 individuals who were participants in the PAC Self-Swab Study and who agreed be contacted for follow-up studies. Individuals will be randomized to use the new NF swab with either a 3 cm or 5 cm insertion depth. After consenting, individuals will receive written instructions and then conduct the self-sampling in private. Staff will take the swab in PreservCyt to the Medical College of Wisconsin Tissue Bank where it will be aliquoted for assessment of cytology and reflex HIV testing at Wisconsin Diagnostic Labs and HPV genotype at Moffitt Cancer Center. We have one objective: To ensure the use of a swab in SOLO that is comparable to the originally proposed swab for SOLO, determine the preliminary performance characteristics of the new NF swab. We have three hypotheses within the objective:

- **H1:** A higher proportion of the new NF swabs with 5 cm insertion will have SCJ cells compared to the NF swab for 3 cm insertion.

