All procedures in the proposed pilot study involve minimal risk. The SOLO pilot uses very similar procedures as did our prior Prevent Anal Cancer Self-Swab Study. When a participant provides consent, they will be thoroughly informed of all pilot study procedures, potential risks, and benefits, and that they can discontinue participation in the study at any time without risk to subsequent care at the place(s) they receive health care. The participant, in a confidential space, will complete the consent in-person. The PI will do the initial consents while being observed by the study coordinator and other study staff; thereafter, the study coordinator and other trained study staff will perform the consents. Before signing, we will ask participants to answer three simple questions that will indicate the participant has understood the consent.

ICFs will be documented in hard copy with participant signatures kept on file in a locked cabinet at the Medical College of Wisconsin.

1. Self-swabbing. When the participant performs a self-swabbing, they will be provided instructions written at a 6th grade reading level, modeled after already-tested self-sampling instructions in the Prevent Anal Cancer Self-Swab Study.¹⁷
2. Sensitive nature of questions. This pilot study will ask sensitive questions about, sexual behavior and disease status during the computer-assisted self-interviews. Thus, names will be kept separate from coded identifiers. All computers will require a password to access files. Computer-assisted self-interviewing will be used so participants can confidentially report sensitive behaviors while minimizing feelings of shame or embarrassment discussing sexual histories. The survey items will mainly come from the

PAC Self-Swab Study surveys, which, in turn, were adapted from validated cervical cancer screening instruments.

3. **PHI access.** Access to all PHI-protected pilot study data will be limited to the PI, study coordinator, other trained and CITI-certified study staff, and clinicians. Data will be destroyed after the pilot study is completed according to federal regulations.

Persons with HIV may be vulnerable; thus, we will ensure that the highest ethical standards will be respected and followed so that benefits are maximized for a diverse set of persons while harms are minimized for all participants. For example, we include a very wide age range of people in enrollment, i.e., 35 years and older.

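### The 5 cm versus 3 cm comparison of pain and acceptability checks interval overlap instead of estimating a difference, and uses no earlier PAC rating even where one could be linked

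*Combined protocol and SAP*

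**What the plan says.** Section H.3.5 has each participant, straight after self-sampling, "rate their acceptability of the cytology screening on a Likert scale and pain on a visual scale". Both ratings are then handled as proportions, with no cut-point given. For the randomised contrast the whole stated analysis is: "The Exact 95% confidence limits surrounding proportions for acceptability and pain will be compared for overlap for 5 cm vs 3 cm insertion depths". Section H.3 names no difference, no model and no covariate.

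Three other places bear on what is known about participants beforehand.

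- **Source of participants.** Section A states: "We will test the new swab with 60 individuals who were participants in the PAC Self-Swab Study". Section E.1 is looser. Recruitment starts with people who "consented into the PAC Self-Swab Study (PRO00032999) and then indicated an interest in a follow-up study (n=126") and is restricted to age 35 or over. It then adds: "If the initial recruitment results in fewer than 60 people, we will recruit by other means".
- **Survey content.** Section K.6.3 says "The survey items will mainly come from the" "PAC Self-Swab Study surveys, which, in turn, were adapted from validated cervical cancer screening instruments".
- **Allocation.** Section F.2 uses simple randomisation: "If the number is .0000 to .4999, the individual will be assigned to the intervention condition". No blocking or stratification is described.

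Section H.2 disclaims power for conclusive statements on any endpoint.

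**The concern.** The depth comparison is the only randomised evidence on the trade-off that section A raises, namely that going deeper might cost acceptability without improving the specimen. Hypothesis H4 expects the two depths to perform similarly. A check for overlapping limits gives no estimate of how different they are, and at this sample size the limits will usually overlap whatever the truth. Overlap could then be read as support for H4.

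With about 30 per arm, individual differences in pain sensitivity also add noise and can be unevenly split by chance. Section H.3.1 will look at whether randomisation succeeded but does not say what follows if an imbalance is found. A PAC rating predates randomisation, so insertion depth cannot have affected it. Where it exists and can be linked, it is a valid baseline covariate, and the plan leaves it unused.

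**Working it through.** The plan gives no effect size, correlation or derivation of its sample size, so there is no figure to reproduce.

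**Inputs from the documents.** N = 60 (sections A and D), so 30 per arm is expected. Under simple randomisation an arm has 25 to 35 people with probability 0.845. The PAC pool is 126 (section E.1), so filling the pilot from PAC alone needs 60/126 = 47.6% uptake, before the age restriction.

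**Assumptions.** Correlation r between PAC and pilot rating: 0 to 0.6. Share f of participants with a linkable rating: 1 or 0.5. True proportions: 0.5 to 0.9. None of these is in the documents.

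**Step 1: the overlap check.** Enumerating all outcomes with 30 per arm and Clopper-Pearson 95% limits:

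| True proportions | Probability that limits do not overlap | Power, two-sided 5% pooled z-test |
|---|---|---|
| 0.5 and 0.5 | 0.0027 | – |
| 0.9 and 0.9 | 0.0008 | – |
| 0.9 and 0.7 | 0.14 | 0.49 |
| 0.9 and 0.6 | 0.39 | 0.78 |
| 0.9 and 0.5 | 0.69 | 0.94 |

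As an example, 27/30 has limits 0.735 to 0.979 and 21/30 has 0.506 to 0.853. They overlap. The difference is 0.20, with an approximate interval of 0.20 ± 1.96 × √(0.9×0.1/30 + 0.7×0.3/30) = 0.20 ± 0.196, or about 0.00 to 0.40. The interval shows that a difference of up to 40 percentage points is compatible with the data; the overlap check does not.

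**Step 2: adjustment, continuous rating.** Without adjustment the 95% half-width is 1.96 × √(2/30) = 0.506 SD. For linear adjustment, variance ratio ≈ (1 − f·r²) × 57/(57 − p). Here 57 = 60 − 3, and p is the number of added terms: 1 if all are linked, 2 if a missing-covariate indicator is needed. The half-width scales with the square root of this ratio.

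| r | All linked: ratio | Half-width (SD) | Half linked: ratio | Half-width (SD) |
|---|---|---|---|---|
| 0 | 57/56 = 1.018 | 0.511 | 57/55 = 1.036 | 0.515 |
| 0.3 | 0.91 × 57/56 = 0.926 | 0.487 | 0.955 × 57/55 = 0.990 | 0.503 |
| 0.5 | 0.75 × 57/56 = 0.763 | 0.442 | 0.875 × 57/55 = 0.907 | 0.482 |
| 0.6 | 0.64 × 57/56 = 0.651 | 0.408 | 0.82 × 57/55 = 0.850 | 0.467 |

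Simulations of the same set-up agree to within about 0.02. At r = 0.3 they give 0.92 to 0.94 with all linked and 0.98 to 1.00 with half linked. This gives the ranges of about 6 to 35% and 0 to 15%.

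**Step 3: adjustment, dichotomised rating.** Here the risk-difference variance ratio is 1 − φ², where φ is the correlation of the two binary ratings implied by a latent normal correlation. With everyone linked and latent correlation 0.3 or 0.5, variance falls by 4% or 11% at a proportion of 0.5, and by 2% or 6% at 0.9.

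**Step 4: choice of model for the Likert item.** A proportional-odds model would not deliver this gain. Adjustment there changes the quantity being estimated and does not shrink its standard error. In simulation (30 + 30, five equal categories, assumed latent shift 0.5 SD, 250 runs) the mean standard error went from 0.475 to 0.485 at r = 0.3 and from 0.477 to 0.496 at r = 0.5. A mean-score or risk difference avoids this.

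**The case against.** A reader might infer that all 60 participants already hold their own PAC pain and acceptability ratings on the same items, so that precision is there for nothing. The documents do not support that.

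- Section E.1 requires PAC consent, not a completed PAC swab and survey, and it allows recruits with no PAC record.
- The statement that items come mainly from PAC describes the survey as a whole, not these two items.
- The planned new-versus-original comparison needs only PAC summary limits, so it does not show that individual records are available.
- Linkage, and permission for it, is not described.
- PAC used a different swab. Its insertion depth and the time elapsed since PAC are not stated, so a moderate correlation cannot be presumed.

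All of this stands, and it is why adjustment is proposed only where a matching rating can be linked.

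It is also fair that the unadjusted randomised comparison is unbiased, and that section H.2 disclaims conclusive inference. The consequence is therefore a less informative and somewhat wider description, not an invalid test. But a pilot that disclaims power relies on estimation, and an overlap check estimates nothing. That part of the point needs no PAC data.

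**Conclusion.** The point holds in two parts of unequal certainty. The firmer part is that H.3.5 gives no estimate of the depth difference, and its overlap check separates the arms with probability only 0.14 at assumed proportions of 0.9 and 0.7. The conditional part is that an available covariate may be going unused. Its value depends on an unknown correlation, the share of participants linked and the scale kept: from a loss of about 2 to 4% of variance at zero correlation to a reduction of about 35% at 0.6 with everyone linked. Only 0 to 15% is gained over correlations of 0.3 to 0.6 if half are linked, and less for dichotomised or near-ceiling ratings. It is a modest improvement to an unbiased comparison. To call it free precision, or to say that every participant has a baseline rating, would go beyond the documents. Sections A and E.1 also differ on whether all 60 are PAC participants and should be reconciled.

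**What to change.** 1. In H.3.5, replace the overlap check for 5 cm versus 3 cm with an estimated 5 cm minus 3 cm difference and its 95% confidence interval. Use a mean difference for the visual pain scale. For the Likert item use a mean-score difference, or a risk difference at a cut-point stated in advance, from a linear or standardised model so that adjusted and unadjusted analyses target the same quantity.
2. Before enrolment, the sponsor should confirm that the PAC pain and acceptability items match the pilot items, that individual PAC records can be linked, and that consent permits it.
3. If so, pre-specify adjustment for the participant's own PAC rating of the matching item, with a missing-covariate indicator for those without one. State in advance the linked share below which only the unadjusted difference and its interval will be reported.

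Step 1 costs only analysis wording. Steps 2 and 3 need a consent-form line with IRB approval, a data link within the team, and one or two degrees of freedom. No new visit, question or participant is required.
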